Foetal death	10055690	PT
Foeticide	10075033	PT
Habitual abortion	10062935	PT
Imminent abortion	10051459	PT
Induced abortion failed	10053191	PT
Induced abortion haemorrhage	10052844	PT
Induced abortion infection	10052845	PT
Molar abortion	10065942	PT
Mycoplasmal postabortal fever	10028479	PT
Post abortion complication	10036244	PT
Post abortion haemorrhage	10036246	PT
Post abortion infection	10061467	PT
Premature baby death	10076700	PT
Prophylaxis of abortion	10065000	PT
Retained products of conception	10038773	PT
Risk of future pregnancy miscarriage	10078342	PT
Selective abortion	10067499	PT
Stillbirth	10042062	PT
Twin reversed arterial perfusion sequence malformation	10073455	PT
Vanishing twin syndrome	10071398	PT

18.3 AESI: Opportunistic Infections

Name	Code	Level	Action
Immunodeficiency disorders NEC	10052739	HLT	Include
Adenoviral infections	10001258	HLT	Include
Allescheria infections	10001753	HLT	Include
Aspergillus infections	10003486	HLT	Include
Atypical mycobacterial infections	10003754	HLT	Include
Blastomyces infections	10005096	HLT	Include
Candida infections	10007134	HLT	Include
Coccidioides infections	10009824	HLT	Include
Cryptococcal infections	10011486	HLT	Include
Cryptosporidia infections	10011499	HLT	Include
Cytomegaloviral infections	10011827	HLT	Include
Fungal infections NEC	10017536	HLT	Include
Histoplasma infections	10020140	HLT	Include
Legionella infections	10024179	HLT	Include
Listeria infections	10024639	HLT	Include
Paracoccidioides infections	10033767	HLT	Include
Pneumocystis infections	10035660	HLT	Include
Pseudallescheria infections	10037104	HLT	Include
Rhinosporidia infections	10039103	HLT	Include
Bartonella infections	10044583	HLT	Include
Toxoplasma infections	10057179	HLT	Include
Tuberculous infections	10044756	HLT	Include
Acinetobacter bacteraemia	10064965	PT	Include
Acinetobacter infection	10051894	PT	Include
Encephalitis protozoal	10061118	PT	Include
Gastrointestinal protozoal infection	10061175	PT	Include
Infection in an immunocompromised host	10021818	PT	Include
Microsporidia infection	10053982	PT	Include
Pelvic inflammatory disease mycoplasmal	10034256	PT	Include
Secondary immunodeficiency	10054979	PT	Include
Trichophytic granuloma	10053419	PT	Include
Vulvovaginal mycotic infection	10064899	PT	Exclude
Balanitis candida	10004074	PT	Exclude
Candida nappy rash	10007135	PT	Exclude
Fungal paronychia	10017540	PT	Exclude
Fungal skin infection	10017543	PT	Exclude
Genital candidiasis	10018143	PT	Exclude
Isosporiasis	10023076	PT	Include
Mucocutaneous candidiasis	10028080	PT	Exclude
Nail candida	10028688	PT	Exclude
Neonatal candida infection	10028924	PT	Exclude
Onychomycosis	10030338	PT	Exclude

████████████████████
████████████████████

████████████████████
████████████████████

Name	Code	Level	Action
Oral candidiasis	10030963	PT	Exclude
Vulvovaginal candidiasis	10047784	PT	Exclude
Microsporium infection	10054121	PT	Include
Skin candida	10054152	PT	Exclude
Salmonella sepsis	10058878	PT	Include
Oral fungal infection	10061324	PT	Exclude
Progressive vaccinia	10069582	PT	Include
Polyoma virus infection	10057200	HLT	Include

[REDACTED]
[REDACTED]

[REDACTED]

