15.5.1 AESI= Infections

Reporting will be regrouped into the 7 following AESI categories.

- AESI = Infections and Infestations

AESI = Infections and infestations is defined by any event belonging to the MedDRA SOC = Infections and Infestations.

- AESI = Severe Infections

AESI = Severe Infections is a custom grouping defined by any serious or severe event belonging to the MedDRA SOC = Infections and Infestations.

Data Handling

[REDACTED]

[REDACTED]

Adverse events collected under the New Diagnosis pages (PREMIERE eCRF only) does not have characteristics for severity being collected. However, AEs collected under the category “Other **severe** infections” will be considered for the definition of the AESI = Severe Infections.

- AESI = Herpetic infections

AESI = Herpetic infections is a custom grouping defined by any events from MedDRA HLT = Herpes viral infections.

- AESI = Opportunistic infections

The medical concept “opportunistic infections (including tuberculosis and PML)” is a custom grouping based on medical assessment. It includes MedDRA Preferred Terms (PTs) associated to viral, protozoal and bacterial infections as well as PTs associated to fungal infections with the exclusion of mucocutaneous and cutaneous fungal infections. Infections as provided by the US Centers of Disease Control (1993 revision) and in the Guidelines for the Prevention and Treatment of Opportunistic Infections in HIV-Infected Adults and Adolescents, <http://aidsinfo.nih.gov/guidelines> are included. PTs pertaining to the HLT ‘Herpes viral infections’ are not included.

This definition will be shortened in the tables footnote to read:

AESI = Opportunistic Infections is based on respective lists available in the context of HIV infections. It includes MedDRA preferred terms (PTs) associated to viral, fungal, protozoal and bacterial infections. PTs pertaining to the HLT ‘Herpes viral infections’ are not included.

The MedDRA terms that will be selected are listed in Appendix 18.3.

- AESI = Herpes zoster infections

AESI = Herpes zoster infections is a custom grouping defined by PTs with the term 'herpes zoster'.

The PTs that will be selected are listed in Appendix 18.4.

- AESI = PML

AESI = PML is a custom grouping defined by any events from MedDRA HLT = Polyomavirus infection.

- AESI = Tuberculosis

AESI = Tuberculosis is a custom grouping defined by any events from MedDRA HLT = Tuberculous infections.

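### Two Include rows in SAP Appendix 18.3 name immunodeficiencies, which contradicts the infections-only definition and footnote of AESI = Opportunistic Infections in Section 15.5.1

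*SAP*

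**What the plan says.** SAP Section 15.5.1 sets up the infection AESIs: "Reporting will be regrouped into the 7 following AESI categories". Opportunistic infections are one of the seven. The full definition reads, in part, "It includes MedDRA Preferred Terms (PTs) associated to viral, protozoal and bacterial infections as well as PTs associated to fungal infections". It leaves out mucocutaneous and cutaneous fungal infections and the herpes viral group. The section then prescribes a shortened table footnote: "It includes MedDRA preferred terms (PTs) associated to viral, fungal, protozoal and bacterial infections". Neither text mentions immunodeficiency.

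The operative selection is delegated: "The MedDRA terms that will be selected are listed in Appendix 18.3". In that appendix, two rows with the action Include are "Immunodeficiency disorders NEC" (HLT, code 10052739) and "Secondary immunodeficiency" (PT, code 10054979).

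PML is a separate category in Section 15.5.1: "AESI = PML is a custom grouping defined by any events from MedDRA HLT = Polyomavirus infection". Appendix 18.3 also includes this HLT, written there as "Polyoma virus infection" (code 10057200), with no PT-level exclusion that names a polyomavirus term.

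Section 15.5 requires, for each AESI, a summary (patient-years, unique events, subjects with an event, crude incidence, 95% CI). It is repeated for serious and fatal events and for four trial groupings. A table by preferred term is also required.

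**The concern.** The list, not the prose, drives the program. If the list admits terms that the prose does not describe, the table counts something other than what its footnote says. A subject with a reported immunodeficiency and no infection would count as a subject with an opportunistic infection.

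The likely counts make this worth correcting. If opportunistic infections are rare in this registry, one or two misplaced events can be a visible share of the row, and a reader who takes the summary line at face value would not know. The SAP also adds a never-exposed reference group (Section 7, Table 1), so these rows will be read side by side.

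The PML row raises a smaller question of the same kind. Its label names one disease, while its definition takes a whole virus group.

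**Working it through.** The plan states no figure to reproduce here. The check sets the two texts side by side and then illustrates the size.

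**Step 1: count the list.** Appendix 18.3 as printed has 50 rows.

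| Level | Include | Exclude | Total |
|---|---|---|---|
| HLT | 23 | 0 | 23 |
| PT | 13 | 14 | 27 |
| Total | 36 | 14 | 50 |

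**Step 2: compare it with the definition.** Two Include rows, one HLT and one PT, name an immunodeficiency and not an infection: 2/36 = 5.6%. Without them 34 Include rows remain. Because one row is a whole HLT, the number of preferred terms involved cannot be counted from the documents.

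**Step 3: ask whether the rows are needed to capture infections.** The list separately includes a preferred term for infection in an immunocompromised host, along with the organism-specific groups. By their names, the two immunodeficiency rows add only events in which the coded term reports no infection.

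**Step 4: trace the outputs.** Every Section 15.5 summary for this AESI would carry such an event. The primary endpoints would not:
- Section 15.1.1 selects by seriousness and relatedness.
- Sections 15.1.2 and 15.1.3 select by system organ class.
- Section 15.1.4 uses lymphocyte counts and a CRF tick box.

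**Step 5: illustrate the size.** Crude incidence is 100 × n/N with an exact Clopper-Pearson interval (Section 15.1.1). The documents give no group sizes or event counts. The upper value, N = 1161, is the number of full participants (Section 7, Table 1). It is an upper bound for the safety population, which leaves out subjects from the drug interaction study. The lower value, N = 600, and all event counts are assumptions. For n = 0 the upper limit is 1 − 0.025^(1/N).

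| Count n | N = 600: % (95% CI) | N = 1161: % (95% CI) |
|---|---|---|
| 0 | 0.00 (0 to 0.61) | 0.00 (0 to 0.32) |
| 1 | 0.17 (0.00 to 0.93) | 0.09 (0.00 to 0.48) |
| 5 | 0.83 (0.27 to 1.93) | 0.43 (0.14 to 1.00) |
| 7 | 1.17 (0.47 to 2.39) | 0.60 (0.24 to 1.24) |

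One extra subject adds 1/600 = 0.17 or 1/1161 = 0.09 percentage points. Two extra on top of five move the row from 0.83% to 1.17%, or from 0.43% to 0.60%.

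**Step 6: PML.** No count is possible, because the documents do not list the terms under the polyomavirus HLT. That it holds terms other than PML is an inference from its name.

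**The case against.** The strongest defence is that the list is deliberate. Section 15.5 describes AESIs as intentionally wide, and Section 15.5.1 calls this list a custom grouping resting on medical judgement. The table by preferred term would show any immunodeficiency event by name, no inference is planned (Section 9.14), and the affected outputs are descriptive. Most of this stands, and it is why the point is small. It does not remove the contradiction. If the rows are intended, the definition and footnote are wrong; if not, the list is. The by-PT table lets a careful reader find the event, but the summary count, percentage and interval still contain it.

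A reader might infer more than the documents support:

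- **That infection risk in the exposed group would be inflated.** The protocol says cladribine causes sustained lymphopenia, so a skew is plausible. Nothing says lymphopenia would be reported or coded as immunodeficiency. Under the current protocol, follow-up collects serious events and all events in two organ classes (blood and lymphatic, neoplasms), which may limit how many non-serious immunodeficiency events are recorded at all.
- **That the count could be 1.5 to 2 times too high.** That needs 2 true events plus 1 or 2 extra: (2+1)/2 = 1.5 and (2+2)/2 = 2. With no extra events the ratio is 1.0. With 10 true events it is 1.1 to 1.2. All these counts are assumed.
- **That the PML row would raise a false signal.** The SAP states the HLT definition openly, prescribes no PML footnote and does not list the HLT's contents, and the by-PT table would show the term. What remains is a label narrower than its definition. The SAP describes no case review for PML, whereas it does for malignancies (Section 15.5.2) and pregnancies (Section 15.2).

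**Conclusion.** The contradiction between Appendix 18.3 and Section 15.5.1 is established from the text alone: 2 of 36 Include rows fall outside the stated definition and the prescribed footnote. As written, the plan would count an immunodeficiency event without infection as an opportunistic infection in the summary tables.

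This is a minor point. It has an effect only if such events occur, and then only on descriptive AESI summaries. Neither the size nor the direction can be derived from the documents. The 0.17 to 0.09 percentage points per extra subject rest on an assumed N of 600 to 1161. The PML item is a secondary labelling remark, not an internal contradiction.

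**What to change.** - **Appendix 18.3:** set the two immunodeficiency rows to Exclude, an action the list already uses, or report them on a separate line outside the opportunistic-infection count.
- **If they are kept on purpose:** say so in the Section 15.5.1 definition and in the table footnote, so that the row describes what it counts.
- **AESI = PML:** either restrict it to the PML preferred term and put other polyomavirus events on their own line, or rename the row as polyomavirus infections. Use one spelling of the HLT in Section 15.5.1 and Appendix 18.3.

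The cost is two row edits in the appendix, or one wording change in the definition and footnote, plus one edit for PML. No new data or new analysis method is needed.

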18.4 AESI Herpes Zoster

Name	Code	Level
Herpes zoster	10019974	PT
Ophthalmic herpes zoster	10030865	PT
Herpes zoster infection neurological	10061208	PT
Herpes zoster oticus	10063491	PT
Herpes zoster disseminated	10065038	PT
Genital herpes zoster	10072210	PT
Herpes zoster pharyngitis	10074245	PT
Herpes zoster meningoencephalitis	10074248	PT
Herpes zoster meningomyelitis	10074251	PT
Herpes zoster necrotising retinopathy	10074253	PT
Herpes zoster meningitis	10074259	PT
Herpes zoster cutaneous disseminated	10074297	PT
Herpes zoster meningoradiculitis	10079327	PT

18.5 Malignant or Unspecified Tumours (SMQ 20000091)

Name	Code	Level
5q minus syndrome	10068532	PT
Acute bilineal leukaemia	10080323	PT
Acute biphenotypic leukaemia	10067399	PT
Acute leukaemia	10000830	PT
Acute leukaemia in remission	10060930	PT
Acute lymphocytic leukaemia	10000846	PT
Acute lymphocytic leukaemia (in remission)	10000847	PT
Acute lymphocytic leukaemia recurrent	10063620	PT
Acute lymphocytic leukaemia refractory	10076866	PT
Acute megakaryocytic leukaemia	10000860	PT
Acute megakaryocytic leukaemia (in remission)	10057194	PT
Acute monocytic leukaemia	10000871	PT
Acute monocytic leukaemia (in remission)	10000872	PT
Acute myeloid leukaemia	10000880	PT
Acute myeloid leukaemia (in remission)	10000881	PT
Acute myeloid leukaemia recurrent	10059034	PT
Acute myelomonocytic leukaemia	10000890	PT
Acute promyelocytic leukaemia	10001019	PT
Acute undifferentiated leukaemia	10073479	PT
Adult T-cell lymphoma/leukaemia	10001413	PT
Adult T-cell lymphoma/leukaemia recurrent	10001416	PT
Adult T-cell lymphoma/leukaemia refractory	10001417	PT
Adult T-cell lymphoma/leukaemia stage I	10001418	PT
Adult T-cell lymphoma/leukaemia stage II	10001419	PT
Adult T-cell lymphoma/leukaemia stage III	10001420	PT
Adult T-cell lymphoma/leukaemia stage IV	10001421	PT
Aleukaemic leukaemia	10001660	PT
Anaplastic large cell lymphoma T- and null-cell types	10002227	PT
Anaplastic large cell lymphoma T- and null-cell types recurrent	10002229	PT
Anaplastic large cell lymphoma T- and null-cell types refractory	10002230	PT
Anaplastic large cell lymphoma T- and null-cell types stage I	10002231	PT
Anaplastic large cell lymphoma T- and null-cell types stage II	10002232	PT
Anaplastic large cell lymphoma T- and null-cell types stage III	10002233	PT
Anaplastic large cell lymphoma T- and null-cell types stage IV	10002234	PT
Anaplastic large-cell lymphoma	10073478	PT
Angiocentric lymphoma	10002411	PT
Angiocentric lymphoma recurrent	10002414	PT
Angiocentric lymphoma refractory	10002415	PT
Angiocentric lymphoma stage I	10002416	PT
Angiocentric lymphoma stage II	10002417	PT
Angiocentric lymphoma stage III	10002418	PT

Name	Code	Level
Angiocentric lymphoma stage IV	10002419	PT
Angioimmunoblastic T-cell lymphoma	10002449	PT
Angioimmunoblastic T-cell lymphoma recurrent	10002452	PT
Angioimmunoblastic T-cell lymphoma refractory	10002453	PT
Angioimmunoblastic T-cell lymphoma stage I	10002454	PT
Angioimmunoblastic T-cell lymphoma stage II	10002455	PT
Angioimmunoblastic T-cell lymphoma stage III	10002456	PT
Angioimmunoblastic T-cell lymphoma stage IV	10002457	PT
B precursor type acute leukaemia	10003890	PT
B-cell lymphoma	10003899	PT
B-cell lymphoma recurrent	10003902	PT
B-cell lymphoma refractory	10003903	PT
B-cell lymphoma stage I	10003904	PT
B-cell lymphoma stage II	10003905	PT
B-cell lymphoma stage III	10003906	PT
B-cell lymphoma stage IV	10003907	PT
B-cell prolymphocytic leukaemia	10073480	PT
B-cell small lymphocytic lymphoma	10003908	PT
B-cell small lymphocytic lymphoma recurrent	10003911	PT
B-cell small lymphocytic lymphoma refractory	10003912	PT
B-cell small lymphocytic lymphoma stage I	10003913	PT
B-cell small lymphocytic lymphoma stage II	10003914	PT
B-cell small lymphocytic lymphoma stage III	10003915	PT
B-cell small lymphocytic lymphoma stage IV	10003916	PT
B-cell type acute leukaemia	10003917	PT
B-cell unclassifiable lymphoma high grade	10003922	PT
B-cell unclassifiable lymphoma low grade	10003923	PT
Blast cell crisis	10053747	PT
Blast crisis in myelogenous leukaemia	10050282	PT
Blastic plasmacytoid dendritic cell neoplasia	10075460	PT
Bone marrow leukaemic cell infiltration	10049557	PT
Bone marrow tumour cell infiltration	10049556	PT
Burkitt's leukaemia	10067184	PT
Burkitt's lymphoma	10006595	PT
Burkitt's lymphoma recurrent	10006598	PT
Burkitt's lymphoma refractory	10006599	PT
Burkitt's lymphoma stage I	10006600	PT
Burkitt's lymphoma stage II	10006601	PT
Burkitt's lymphoma stage III	10006602	PT
Burkitt's lymphoma stage IV	10006603	PT
Central nervous system leukaemia	10066231	PT
Central nervous system lymphoma	10007953	PT
Chloroma	10008583	PT
Chloroma (in remission)	10008584	PT

Name	Code	Level
Chronic eosinophilic leukaemia	10065854	PT
Chronic leukaemia	10008943	PT
Chronic leukaemia in remission	10061042	PT
Chronic lymphocytic leukaemia	10008958	PT
Chronic lymphocytic leukaemia (in remission)	10008959	PT
Chronic lymphocytic leukaemia recurrent	10008961	PT
Chronic lymphocytic leukaemia refractory	10008962	PT
Chronic lymphocytic leukaemia stage 0	10008963	PT
Chronic lymphocytic leukaemia stage 1	10008964	PT
Chronic lymphocytic leukaemia stage 2	10008965	PT
Chronic lymphocytic leukaemia stage 3	10008966	PT
Chronic lymphocytic leukaemia stage 4	10008967	PT
Chronic lymphocytic leukaemia transformation	10058717	PT
Chronic myeloid leukaemia	10009013	PT
Chronic myeloid leukaemia (in remission)	10009014	PT
Chronic myeloid leukaemia recurrent	10075081	PT
Chronic myeloid leukaemia transformation	10068232	PT
Chronic myelomonocytic leukaemia	10009018	PT
Chronic myelomonocytic leukaemia (in remission)	10009019	PT
Composite lymphoma	10073957	PT
Cutaneous lymphoma	10079945	PT
Diffuse large B-cell lymphoma	10012818	PT
Diffuse large B-cell lymphoma recurrent	10012821	PT
Diffuse large B-cell lymphoma refractory	10012822	PT
Diffuse large B-cell lymphoma stage I	10012823	PT
Diffuse large B-cell lymphoma stage II	10012824	PT
Diffuse large B-cell lymphoma stage III	10012825	PT
Diffuse large B-cell lymphoma stage IV	10012826	PT
Disseminated large cell lymphoma	10054951	PT
Double hit lymphoma	10080202	PT
Enteropathy-associated T-cell lymphoma	10073481	PT
Eosinophilic leukaemia	10014958	PT
Epstein-Barr virus associated lymphoma	10071441	PT
Erythraemic myelosis (in remission)	10015246	PT
Erythroleukaemia	10015281	PT
Extranodal marginal zone B-cell lymphoma (MALT type)	10061850	PT
Extranodal marginal zone B-cell lymphoma (MALT type) recurrent	10015823	PT
Extranodal marginal zone B-cell lymphoma (MALT type) refractory	10015824	PT
Extranodal marginal zone B-cell lymphoma (MALT type) stage I	10015825	PT
Extranodal marginal zone B-cell lymphoma (MALT type) stage II	10015826	PT
Extranodal marginal zone B-cell lymphoma (MALT type) stage III	10015827	PT
Extranodal marginal zone B-cell lymphoma (MALT type) stage IV	10015828	PT
Follicle centre lymphoma diffuse small cell lymphoma	10061957	PT
Follicle centre lymphoma diffuse small cell lymphoma recurrent	10016897	PT

Name	Code	Level
Follicle centre lymphoma diffuse small cell lymphoma refractory	10016898	PT
Follicle centre lymphoma diffuse small cell lymphoma stage I	10016899	PT
Follicle centre lymphoma diffuse small cell lymphoma stage II	10016900	PT
Follicle centre lymphoma diffuse small cell lymphoma stage III	10016901	PT
Follicle centre lymphoma diffuse small cell lymphoma stage IV	10016902	PT
Follicle centre lymphoma, follicular grade I, II, III	10061170	PT
Follicle centre lymphoma, follicular grade I, II, III recurrent	10016905	PT
Follicle centre lymphoma, follicular grade I, II, III refractory	10016906	PT
Follicle centre lymphoma, follicular grade I, II, III stage I	10016907	PT
Follicle centre lymphoma, follicular grade I, II, III stage II	10016908	PT
Follicle centre lymphoma, follicular grade I, II, III stage III	10016909	PT
Follicle centre lymphoma, follicular grade I, II, III stage IV	10016910	PT
Follicular dendritic cell sarcoma	10075332	PT
Gastrointestinal lymphoma	10017973	PT
Haematological malignancy	10066476	PT
Hairy cell leukaemia	10019053	PT
Hairy cell leukaemia recurrent	10077403	PT
Hepatosplenic T-cell lymphoma	10066957	PT
High grade B-cell lymphoma Burkitt-like lymphoma	10020067	PT
High grade B-cell lymphoma Burkitt-like lymphoma recurrent	10020070	PT
High grade B-cell lymphoma Burkitt-like lymphoma refractory	10020071	PT
High grade B-cell lymphoma Burkitt-like lymphoma stage I	10020072	PT
High grade B-cell lymphoma Burkitt-like lymphoma stage II	10020073	PT
High grade B-cell lymphoma Burkitt-like lymphoma stage III	10020074	PT
High grade B-cell lymphoma Burkitt-like lymphoma stage IV	10020075	PT
High-grade B-cell lymphoma	10080215	PT
Histiocytic medullary reticulosis	10068785	PT
Histiocytic sarcoma	10076876	PT
Hodgkin's disease	10020206	PT
Hodgkin's disease lymphocyte depletion stage I site unspecified	10020208	PT
Hodgkin's disease lymphocyte depletion stage I subdiaphragm	10020209	PT
Hodgkin's disease lymphocyte depletion stage I supradiaphragm	10020210	PT
Hodgkin's disease lymphocyte depletion stage II site unspecified	10020211	PT
Hodgkin's disease lymphocyte depletion stage II subdiaphragm	10020212	PT
Hodgkin's disease lymphocyte depletion stage II supradiaphragm	10020213	PT
Hodgkin's disease lymphocyte depletion type recurrent	10020215	PT
Hodgkin's disease lymphocyte depletion type refractory	10020216	PT
Hodgkin's disease lymphocyte depletion type stage III	10020217	PT
Hodgkin's disease lymphocyte depletion type stage IV	10020218	PT
Hodgkin's disease lymphocyte depletion type stage unspecified	10020219	PT
Hodgkin's disease lymphocyte predominance stage I site unspec	10020220	PT
Hodgkin's disease lymphocyte predominance stage I subdiaphragm	10020221	PT
Hodgkin's disease lymphocyte predominance stage I supradiaphragm	10020222	PT
Hodgkin's disease lymphocyte predominance stage II site unspec	10020223	PT

Name	Code	Level
Hodgkin's disease lymphocyte predominance stage II subdiaphragm	10020224	PT
Hodgkin's disease lymphocyte predominance stage II supradiaphragm	10020225	PT
Hodgkin's disease lymphocyte predominance type recurrent	10020227	PT
Hodgkin's disease lymphocyte predominance type refractory	10020228	PT
Hodgkin's disease lymphocyte predominance type stage III	10020229	PT
Hodgkin's disease lymphocyte predominance type stage IV	10020230	PT
Hodgkin's disease lymphocyte predominance type stage unspecified	10020231	PT
Hodgkin's disease mixed cellularity recurrent	10020233	PT
Hodgkin's disease mixed cellularity refractory	10020234	PT
Hodgkin's disease mixed cellularity stage I site unspecified	10020235	PT
Hodgkin's disease mixed cellularity stage I subdiaphragmatic	10020236	PT
Hodgkin's disease mixed cellularity stage I supradiaphragmatic	10020237	PT
Hodgkin's disease mixed cellularity stage II subdiaphragmatic	10020238	PT
Hodgkin's disease mixed cellularity stage II supradiaphragmatic	10020239	PT
Hodgkin's disease mixed cellularity stage III	10020240	PT
Hodgkin's disease mixed cellularity stage IV	10020241	PT
Hodgkin's disease mixed cellularity stage unspecified	10020242	PT
Hodgkin's disease nodular sclerosis	10020244	PT
Hodgkin's disease nodular sclerosis recurrent	10020245	PT
Hodgkin's disease nodular sclerosis refractory	10020246	PT
Hodgkin's disease nodular sclerosis stage I	10073535	PT
Hodgkin's disease nodular sclerosis stage II	10073534	PT
Hodgkin's disease nodular sclerosis stage III	10020252	PT
Hodgkin's disease nodular sclerosis stage IV	10020253	PT
Hodgkin's disease recurrent	10020266	PT
Hodgkin's disease refractory	10020267	PT
Hodgkin's disease stage I	10020268	PT
Hodgkin's disease stage II	10020269	PT
Hodgkin's disease stage III	10020270	PT
Hodgkin's disease stage IV	10061597	PT
Hodgkin's disease unclassifiable	10020271	PT
Immunoblastic lymphoma	10053574	PT
Intestinal T-cell lymphoma recurrent	10022706	PT
Intestinal T-cell lymphoma refractory	10022707	PT
Intestinal T-cell lymphoma stage I	10022708	PT
Intestinal T-cell lymphoma stage II	10022709	PT
Intestinal T-cell lymphoma stage III	10022710	PT
Intestinal T-cell lymphoma stage IV	10022711	PT
Juvenile chronic myelomonocytic leukaemia	10023249	PT
Leptomeningeal myelomatosis	10078282	PT
Leukaemia	10024288	PT
Leukaemia basophilic	10024293	PT
Leukaemia cutis	10053180	PT
Leukaemia granulocytic	10024299	PT

Name	Code	Level
Leukaemia in remission	10061220	PT
Leukaemia monocytic	10024305	PT
Leukaemia recurrent	10062489	PT
Leukaemic cardiac infiltration	10077563	PT
Leukaemic infiltration	10069360	PT
Leukaemic infiltration extramedullary	10067117	PT
Leukaemic infiltration gingiva	10067431	PT
Leukaemic infiltration hepatic	10058671	PT
Leukaemic infiltration ovary	10075853	PT
Leukaemic infiltration pulmonary	10052368	PT
Leukaemic infiltration renal	10069359	PT
Leukaemic lymphoma	10024325	PT
Leukaemic retinopathy	10059239	PT
Lymphangiosarcoma	10025223	PT
Lymphangiosis carcinomatosa	10053132	PT
Lymphocytic leukaemia	10025270	PT
Lymphocytic lymphoma	10052178	PT
Lymphoid leukaemia (in remission)	10025300	PT
Lymphoma	10025310	PT
Lymphoma AIDS related	10025312	PT
Lymphoma transformation	10064344	PT
Lymphoplasmacytoid lymphoma/immunocytoma	10025342	PT
Lymphoplasmacytoid lymphoma/immunocytoma recurrent	10025345	PT
Lymphoplasmacytoid lymphoma/immunocytoma refractory	10025346	PT
Lymphoplasmacytoid lymphoma/immunocytoma stage I	10025347	PT
Lymphoplasmacytoid lymphoma/immunocytoma stage II	10025348	PT
Lymphoplasmacytoid lymphoma/immunocytoma stage III	10025349	PT
Lymphoplasmacytoid lymphoma/immunocytoma stage IV	10025350	PT
Malignant histiocytosis	10025581	PT
Malignant lymphoid neoplasm	10061240	PT
Malignant lymphoma unclassifiable high grade	10025635	PT
Malignant lymphoma unclassifiable low grade	10025636	PT
Malignant mast cell neoplasm	10025638	PT
Malignant neoplasm of thymus	10026533	PT
Malignant splenic neoplasm	10026702	PT
Mantle cell lymphoma	10061275	PT
Mantle cell lymphoma recurrent	10026800	PT
Mantle cell lymphoma refractory	10026801	PT
Mantle cell lymphoma stage I	10026802	PT
Mantle cell lymphoma stage II	10026803	PT
Mantle cell lymphoma stage III	10026804	PT
Mantle cell lymphoma stage IV	10026805	PT
Marginal zone lymphoma	10076596	PT
Marginal zone lymphoma recurrent	10077533	PT

Name	Code	Level
Marginal zone lymphoma refractory	10077534	PT
Marginal zone lymphoma stage I	10077529	PT
Marginal zone lymphoma stage II	10077530	PT
Marginal zone lymphoma stage III	10077531	PT
Marginal zone lymphoma stage IV	10077532	PT
Mastocytic leukaemia	10056450	PT
Mature B-cell type acute leukaemia	10026945	PT
Metastases to bone marrow	10051662	PT
Metastases to lymph nodes	10027459	PT
Metastases to spleen	10051682	PT
Metastatic lymphoma	10071541	PT
Minimal residual disease	10079987	PT
Monocytic leukaemia in remission	10061295	PT
Mycosis fungoides	10028483	PT
Mycosis fungoides recurrent	10028501	PT
Mycosis fungoides refractory	10028502	PT
Mycosis fungoides stage I	10028503	PT
Mycosis fungoides stage II	10028504	PT
Mycosis fungoides stage III	10028505	PT
Mycosis fungoides stage IV	10028506	PT
Myeloblastoma	10051141	PT
Myeloid leukaemia	10028549	PT
Myeloid leukaemia in remission	10061301	PT
Natural killer-cell leukaemia	10028811	PT
Natural killer-cell lymphoblastic lymphoma	10058975	PT
Neonatal leukaemia	10028958	PT
Nodal marginal zone B-cell lymphoma	10029460	PT
Nodal marginal zone B-cell lymphoma recurrent	10029463	PT
Nodal marginal zone B-cell lymphoma refractory	10029464	PT
Nodal marginal zone B-cell lymphoma stage I	10029465	PT
Nodal marginal zone B-cell lymphoma stage II	10029466	PT
Nodal marginal zone B-cell lymphoma stage III	10029467	PT
Nodal marginal zone B-cell lymphoma stage IV	10029468	PT
Nodular lymphocyte predominant Hodgkin lymphoma	10080201	PT
Non-Hodgkin's lymphoma	10029547	PT
Non-Hodgkin's lymphoma metastatic	10071535	PT
Non-Hodgkin's lymphoma recurrent	10029600	PT
Non-Hodgkin's lymphoma refractory	10029601	PT
Non-Hodgkin's lymphoma stage I	10029602	PT
Non-Hodgkin's lymphoma stage II	10029603	PT
Non-Hodgkin's lymphoma stage III	10029604	PT
Non-Hodgkin's lymphoma stage IV	10029605	PT
Non-Hodgkin's lymphoma transformed recurrent	10061871	PT
Non-Hodgkin's lymphoma unspecified histology aggressive	10063908	PT

Name	Code	Level
Non-Hodgkin's lymphoma unspecified histology aggressive recurrent	10029609	PT
Non-Hodgkin's lymphoma unspecified histology aggressive refractory	10029610	PT
Non-Hodgkin's lymphoma unspecified histology aggressive stage I	10029611	PT
Non-Hodgkin's lymphoma unspecified histology aggressive stage II	10029612	PT
Non-Hodgkin's lymphoma unspecified histology aggressive stage III	10029613	PT
Non-Hodgkin's lymphoma unspecified histology aggressive stage IV	10029614	PT
Non-Hodgkin's lymphoma unspecified histology indolent	10065856	PT
Non-Hodgkin's lymphoma unspecified histology indolent stage I	10029622	PT
Non-Hodgkin's lymphoma unspecified histology indolent stage II	10029623	PT
Non-Hodgkin's lymphoma unspecified histology indolent stage III	10029624	PT
Non-Hodgkin's lymphoma unspecified histology indolent stage IV	10029625	PT
Ocular lymphoma	10075324	PT
Peripheral T-cell lymphoma unspecified	10034623	PT
Peripheral T-cell lymphoma unspecified recurrent	10034625	PT
Peripheral T-cell lymphoma unspecified refractory	10034626	PT
Peripheral T-cell lymphoma unspecified stage I	10034627	PT
Peripheral T-cell lymphoma unspecified stage II	10034628	PT
Peripheral T-cell lymphoma unspecified stage III	10034629	PT
Peripheral T-cell lymphoma unspecified stage IV	10034630	PT
Plasma cell leukaemia	10035222	PT
Plasma cell leukaemia in remission	10060406	PT
Plasma cell myeloma	10035226	PT
Plasma cell myeloma in remission	10073132	PT
Plasma cell myeloma recurrent	10073133	PT
Plasmablastic lymphoma	10065039	PT
Plasmacytoma	10035484	PT
Precursor B-lymphoblastic lymphoma	10036523	PT
Precursor B-lymphoblastic lymphoma recurrent	10060910	PT
Precursor B-lymphoblastic lymphoma refractory	10060911	PT
Precursor B-lymphoblastic lymphoma stage I	10036532	PT
Precursor B-lymphoblastic lymphoma stage II	10036533	PT
Precursor B-lymphoblastic lymphoma stage III	10036534	PT
Precursor B-lymphoblastic lymphoma stage IV	10036535	PT
Precursor T-lymphoblastic lymphoma/leukaemia	10036543	PT
Precursor T-lymphoblastic lymphoma/leukaemia recurrent	10036546	PT
Precursor T-lymphoblastic lymphoma/leukaemia refractory	10036547	PT
Precursor T-lymphoblastic lymphoma/leukaemia stage I	10036548	PT
Precursor T-lymphoblastic lymphoma/leukaemia stage II	10036549	PT
Precursor T-lymphoblastic lymphoma/leukaemia stage III	10036550	PT
Precursor T-lymphoblastic lymphoma/leukaemia stage IV	10036551	PT
Primary breast lymphoma	10081036	PT
Primary cardiac lymphoma	10075993	PT
Primary effusion lymphoma	10065857	PT
Primary gastrointestinal follicular lymphoma	10078972	PT

Name	Code	Level
Primary mediastinal large B-cell lymphoma	10036710	PT
Primary mediastinal large B-cell lymphoma recurrent	10036713	PT
Primary mediastinal large B-cell lymphoma refractory	10036714	PT
Primary mediastinal large B-cell lymphoma stage I	10036715	PT
Primary mediastinal large B-cell lymphoma stage II	10036716	PT
Primary mediastinal large B-cell lymphoma stage III	10036717	PT
Primary mediastinal large B-cell lymphoma stage IV	10036718	PT
Polymphocytic leukaemia	10036888	PT
Richter's syndrome	10058728	PT
Splenic marginal zone lymphoma	10062113	PT
Splenic marginal zone lymphoma recurrent	10041652	PT
Splenic marginal zone lymphoma refractory	10041653	PT
Splenic marginal zone lymphoma stage I	10041654	PT
Splenic marginal zone lymphoma stage II	10041655	PT
Splenic marginal zone lymphoma stage III	10041656	PT
Splenic marginal zone lymphoma stage IV	10041657	PT
T-cell chronic lymphocytic leukaemia	10042970	PT
T-cell lymphoma	10042971	PT
T-cell lymphoma recurrent	10042979	PT
T-cell lymphoma refractory	10042980	PT
T-cell lymphoma stage I	10042981	PT
T-cell lymphoma stage II	10042982	PT
T-cell lymphoma stage III	10042983	PT
T-cell lymphoma stage IV	10042984	PT
T-cell prolymphocytic leukaemia	10042985	PT
T-cell type acute leukaemia	10042987	PT
T-cell unclassifiable lymphoma high grade	10042989	PT
T-cell unclassifiable lymphoma low grade	10042990	PT
Thymic cancer metastatic	10055108	PT
Thymoma malignant	10061031	PT
Thymoma malignant recurrent	10043674	PT
Thyroid B-cell lymphoma	10072613	PT
Transformation to acute myeloid leukaemia	10079107	PT
Triple hit lymphoma	10080200	PT
Waldenstrom's macroglobulinaemia	10047801	PT
Waldenstrom's macroglobulinaemia recurrent	10047804	PT
Waldenstrom's macroglobulinaemia refractory	10047805	PT
Waldenstrom's macroglobulinaemia stage I	10047806	PT
Waldenstrom's macroglobulinaemia stage II	10047807	PT
Waldenstrom's macroglobulinaemia stage III	10047808	PT
Waldenstrom's macroglobulinaemia stage IV	10047809	PT
Abdominal wall neoplasm malignant	10071023	PT
Acinar cell carcinoma of pancreas	10073363	PT
Acinic cell carcinoma of salivary gland	10073369	PT

Name	Code	Level
Acral lentiginous melanoma	10000583	PT
Acral lentiginous melanoma stage I	10000585	PT
Acral lentiginous melanoma stage II	10000586	PT
Acral lentiginous melanoma stage III	10000587	PT
Acral lentiginous melanoma stage IV	10000588	PT
Adenocarcinoma	10001141	PT
Adenocarcinoma gastric	10001150	PT
Adenocarcinoma of appendix	10073359	PT
Adenocarcinoma of colon	10001167	PT
Adenocarcinoma of salivary gland	10068068	PT
Adenocarcinoma of the cervix	10001197	PT
Adenocarcinoma pancreas	10052747	PT
Adenoid cystic carcinoma	10053231	PT
Adenoid cystic carcinoma of external auditory canal	10078057	PT
Adenoid cystic carcinoma of salivary gland	10073370	PT
Adenosquamous carcinoma of the cervix	10001244	PT
Adenosquamous carcinoma of vagina	10073978	PT
Adenosquamous cell carcinoma	10068873	PT
Adenosquamous cell lung cancer	10001245	PT
Adenosquamous cell lung cancer recurrent	10001247	PT
Adenosquamous cell lung cancer stage 0	10001248	PT
Adenosquamous cell lung cancer stage I	10001249	PT
Adenosquamous cell lung cancer stage II	10001250	PT
Adenosquamous cell lung cancer stage III	10001251	PT
Adenosquamous cell lung cancer stage IV	10001254	PT
Adrenal gland cancer	10073152	PT
Adrenal gland cancer metastatic	10055095	PT
Adrenocortical carcinoma	10001388	PT
Aesthesioneuroblastoma	10001433	PT
Alveolar rhabdomyosarcoma	10065867	PT
Alveolar soft part sarcoma	10001882	PT
Alveolar soft part sarcoma metastatic	10001884	PT
Alveolar soft part sarcoma recurrent	10001887	PT
Anal cancer	10061424	PT
Anal cancer metastatic	10055096	PT
Anal cancer recurrent	10002133	PT
Anal cancer stage 0	10002134	PT
Anal cancer stage I	10002135	PT
Anal cancer stage II	10002136	PT
Anal cancer stage III	10002137	PT
Anal cancer stage IV	10002138	PT
Anal squamous cell carcinoma	10073358	PT
Anaplastic astrocytoma	10002224	PT
Anaplastic meningioma	10073127	PT

Name	Code	Level
Anaplastic oligodendroglioma	10073128	PT
Anaplastic thyroid cancer	10002240	PT
Angiocentric glioma	10073129	PT
Angiosarcoma	10002476	PT
Angiosarcoma metastatic	10002477	PT
Angiosarcoma non-metastatic	10057700	PT
Angiosarcoma recurrent	10002480	PT
Apocrine breast carcinoma	10066206	PT
Appendix cancer	10073360	PT
Astrocytoma	10003571	PT
Astrocytoma malignant	10060971	PT
Atypical teratoid/rhabdoid tumour of CNS	10065907	PT
Basal cell carcinoma	10004146	PT
Basosquamous carcinoma	10004178	PT
Basosquamous carcinoma of skin	10004179	PT
Bile duct adenocarcinoma	10004585	PT
Bile duct adenosquamous carcinoma	10004589	PT
Bile duct cancer	10004593	PT
Bile duct cancer recurrent	10004596	PT
Bile duct cancer stage 0	10059384	PT
Bile duct cancer stage I	10059373	PT
Bile duct cancer stage II	10059374	PT
Bile duct cancer stage III	10059375	PT
Bile duct cancer stage IV	10059376	PT
Bile duct squamous cell carcinoma	10004633	PT
Biliary cancer metastatic	10055111	PT
Biphasic mesothelioma	10073062	PT
Bladder adenocarcinoma recurrent	10004986	PT
Bladder adenocarcinoma stage 0	10004987	PT
Bladder adenocarcinoma stage I	10004988	PT
Bladder adenocarcinoma stage II	10004989	PT
Bladder adenocarcinoma stage III	10004990	PT
Bladder adenocarcinoma stage IV	10004991	PT
Bladder adenocarcinoma stage unspecified	10004992	PT
Bladder cancer	10005003	PT
Bladder cancer recurrent	10005005	PT
Bladder cancer stage 0, with cancer in situ	10005006	PT
Bladder cancer stage 0, without cancer in situ	10005007	PT
Bladder cancer stage I, with cancer in situ	10005008	PT
Bladder cancer stage I, without cancer in situ	10005009	PT
Bladder cancer stage II	10005010	PT
Bladder cancer stage III	10005011	PT
Bladder cancer stage IV	10005012	PT
Bladder squamous cell carcinoma recurrent	10005075	PT

Name	Code	Level
Bladder squamous cell carcinoma stage 0	10005076	PT
Bladder squamous cell carcinoma stage I	10005077	PT
Bladder squamous cell carcinoma stage II	10005078	PT
Bladder squamous cell carcinoma stage III	10005079	PT
Bladder squamous cell carcinoma stage IV	10005080	PT
Bladder squamous cell carcinoma stage unspecified	10005081	PT
Bladder transitional cell carcinoma	10005084	PT
Bladder transitional cell carcinoma metastatic	10071664	PT
Bladder transitional cell carcinoma recurrent	10066750	PT
Bladder transitional cell carcinoma stage 0	10066749	PT
Bladder transitional cell carcinoma stage I	10066751	PT
Bladder transitional cell carcinoma stage II	10066753	PT
Bladder transitional cell carcinoma stage III	10066754	PT
Bladder transitional cell carcinoma stage IV	10066752	PT
Bone cancer	10005949	PT
Bone cancer metastatic	10055101	PT
Bone giant cell tumour malignant	10073106	PT
Bone sarcoma	10006007	PT
Bowen's disease	10006059	PT
